- Process for Aim #3: Patients with ARDS will be analyzed based on hypoxemia conditions (as defined by their PaO₂ to FiO₂ ratio) using 3 classifications: mild (201-300), moderate (101-200), and severe (≤100). This subgroup analysis will evaluate protocol implementation of the high versus low positive end expiratory pressure (PEEP) protocol and assess relationship with patient outcomes. Data from Intermountain ICUs in 2014 have shown that approximately 500 patients meet the criteria for "severe" hypoxemia. Patients with moderate and severe hypoxemia will be identified to determine the frequency of high PEEP protocol usage (which is the recommendation in the protocol). Implementation of the high PEEP protocol will be based upon clinician discretion. We will assess outcomes in the 4 hypoxemia sub-groups noted above using a stratified Kaplan–Meier curve to determine differences in mortality using log rank statistics.
- Hypothesis 3: A high PEEP strategy in patients with moderate to severe hypoxemia and ARDS will improve outcomes.

Specific Aim #4: Measure compliance of the computerized lung protective ventilation protocol after implementation across Intermountain Healthcare's 11

hospitals that manage mechanically ventilated patients with acute respiratory failure.

- Process for Aim #4: Tool utilization and compliance will test the ability
 of a healthcare system to introduce this proven lung protective
 ventilation protocol in a new electronic medical record in a controlled
 clinical environment. To ensure that this is successful, [name] will
 identify local champions to train and educate the healthcare providers.
- Hypothesis 4: Healthcare providers will utilize the computerized ventilation protocol and will comply with protocol instructions.

Study Design:

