This is an observational quality improvement study comparing outcomes before, and after, implementation of a proven lung protective ventilation protocol in an electronic medical record system, iCentra, that will be implemented in phases across Intermountain Healthcare hospitals. A phased implementation with a twomonth washout period will be used to evaluate the primary outcome of interest, ventilator free days (VFDs) to 28 days. Secondary outcomes will include: use of the protocol by clinicians, compliance with protocol instructions, hospital discharge disposition, hospital, 30-day, and 90-day mortality, time to first ICU activity, hospital length of stay, ICU length of stay, heath care utilization, quality of life, and costs of care. As the iCentra electronic medical record is implemented at Intermountain Healthcare hospitals, clinicians will have the opportunity to use the computerized lung protective ventilation protocol, or to order mechanical ventilation settings independently. This is an observational study designed to measure how often the computerized lung protective ventilation protocol will be ordered, compliance with the instructions of the protocol, and clinical outcomes among patients who are managed with the protocol. Physicians may choose to use the protocol on intubated patients requiring mechanical ventilation or they may choose to order other specific mechanical ventilator settings.

A meta-analysis of mechanically ventilated patients without the acute respiratory distress syndrome (ARDS) reported that the cohort who received mechanical ventilation with initial tidal volumes between 6 and 10 ml/kg PBW had mean VFD of 21.9 (SD = 7.8). Using the distribution reported in the meta-analysis as the baseline for an a priori analysis, the current authors demonstrated that 3,900 patients would be sufficient to detect a 1.5-day increase in mean VFD with 80%

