Those to be enrolled must have respiratory failure requiring intubation and initiation of mechanical ventilation. Patients will be divided into two different groups: those patients who are managed with the computerized lung protective ventilation protocol as ordered by the attending physician and those patients managed with physician specified mechanical ventilation settings.

Compensation

Subjects will not be compensated for participating in this study.

Sample Size

The minimum sufficient sample size to detect a significant change in VFD was computed across a range of effects and heterogeneity. We estimate about 3,900 subjects would be sufficient to detect a 1.5-day increase in mean VFD with 80% power (*ICC* = 0.10) from a baseline of 21.9 VFD (SD=7.8) with a one-tailed test (**Table 3**).

Table 3. Minimum sample size for increase in mean VFD

ICC	1 day	1.5	2 day
		day	
0.01	6,800	3,200	2,300
0.10	8,500	3,900	2,300
0.20	8,300	4,000	2,400

The baseline VFD data for the power analysis was based on reported data from a meta-analysis of the association between tidal volume size and sedation needs

in patients without ARDS²⁵ among those who received initial tidal volumes between 6 and 10 ml/kg PBW – a demographic representative of our study population. The power analyses accounted for expected imbalance of patient enrollment (**Table 4**),^{26,27} heterogeneity among clusters,²⁸ and allowed for a variety of time effects (**Equation 1**).²⁹ This avoided artificial inflation of power at the study design stage.³⁰

The VFD y_{ikt} for each patient were simulated via a linear equation adapted from Hussy *et al.*³¹ with the addition of quadratic time effects:

$$y_{ikt} = \mu + \alpha_k + \beta_1 t + \beta_2 t^2 + \theta x_{ikt} + e_{ikt},$$
 (1)

where μ and e_{ikt} , were derived from the distribution of VFD reported in the metaanalysis by Serpa Neto *et al.*²⁵, θ varied from 1 to 2 per [name]'s instructions, α_k are the hospital-level random intercepts, $\beta = (\beta_1, \beta_2)$ is a vector of quadratic time effects, x_{ikt} is the initial tidal volume size for the *i*th subject in the *k*th cluster at time *t*.

	Volume	Proportion
McKay-Dee	542	0.1584
Utah Valley	608	0.1778
American Fork	68	0.0199
Dixie	479	0.14
Valley View	60	0.0175
IMC	1409	0.4119
LDS	206	0.0602
Riverton	49	0.0143

Table 4. Volume of mechanically ventilated patients in 2014

Methods/Procedures:

Research Strategy for Specific Aims 1 and 2

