- Tidal Volume per Predicted Body Weight
- Measured Volume per Predicted Body Weight
- Difference between Tidal Volume per PBW and Measured Volume per PBW
- Difference between admission date and death date
- 30 Day Mortality
- 60 Day Mortality
- 90 Day Mortality
- Initial Arterial Blood Gas recorded during hospital stay
- PaO2 (measured)
- PaO2 (corrected)
- FiO2
- PaO2 / FiO2

Data Analysis:

Primary Outcomes

The primary outcome will be VFD to day 28. Patients who experience death within 28 days of ICU admission will be counted as having zero VFD.

Secondary outcomes will include: hospital discharge disposition; hospital, 30-day, and 90-day mortality; time to first ICU activity; hospital, ICU length of stay; protocol compliance; implementation of a high PEEP strategy in patients with PaO_2/FIO_2 ratios \leq 200; heath care utilization; quality of life (SF-36 or similar); and costs of care.

Data Analysis

Descriptive analyses will include Fisher's exact test and Pearson's chi-square test for comparing pairs of binomially distributed variables with and without sparse cells, respectively. Wilcoxon rank sum test, a nonparametric analogue of Student's *t* test, will be used to compare non-Gaussian, continuous distributions. Bootstrapped Kolmogorov-Smirnov (K-S) test will compare distributions of

ordinal, discrete data. The bootstrapped K-S test is able to handle instances in which many ties are present between distributions.²⁴

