Generalized linear mixed models (GLMM) with hospital-level random intercepts and an identify link function will be used to measure the effect of initial tidal volume size on VFD. It is proposed to measure the treatment as a continuous variable (rather than as a dichotomous indicator of whether the mechanically ventilated patient was cared for at a post-intervention site) in order to account for the variable "usual care" practices of tidal volume size. The protocol will be phased sequentially in a non-randomized phased implementation manner. Since it is hypothesized that the bundle will improve care and, resultantly, decrease duration of time on ventilator, statistical significance will be determined by a one-tailed, 5% significance test. Heterogeneity among clusters will also be measured and accounted for random intercepts. Potential secular trends will be adjusted for by inclusion of quadratic time effects, which would capture a variety of time effects – from linear to bell-shaped. Patient-specific confounders will be controlled for by additive inclusion of a matrix of patient-level covariates.

Mitigation Plans and Interim Analysis

We plan an interim analysis for futility and efficacy at the end of the third step, following the successful phasing in of the second cluster. If the mean VFD following implementation of the bundle is equivalent to the mean VFD prior to implementation (according to the two one-sided test procedure with 99% confidence having an equivalence margin of four hours) then futility will be declared and further data collection will cease. Conversely, if the mean VFD following implementation has increased by more than 2 days (according to a one-sided hypothesis test with 99% confidence), efficacy will have been established and further data collection will also cease.

Data Sharing:

Development of the ventilation protocol in iCentra for mechanical ventilation will likely increase the number of VFDs, decrease healthcare utilization and decrease cost. To ensure that the proposal deliverables are met, we have designed the following dissemination plan:

Internal Strategic Planning

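### The SD of 7.8 behind 80% power at about 3,900 comes from patients without ARDS and is not justified for a study that enrols ARDS patients and scores deaths as zero

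*Protocol*

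**What the plan says.** - **Sample size (Research Subjects, Sample Size):** "We estimate about 3,900 subjects would be sufficient to detect a 1.5-day increase in mean VFD with 80% power" at ICC 0.10, from "a baseline of 21.9 VFD (SD=7.8) with a one-tailed test". The Data Analysis section adds that "statistical significance will be determined by a one-tailed, 5% significance test".
- **Source of mean and SD (Study Design; Sample Size):** a meta-analysis of ventilated patients without ARDS, in the group with initial tidal volumes of 6 to 10 ml/kg PBW. Sample Size calls this group "a demographic representative of our study population".
- **Who is enrolled (Inclusion and Exclusion Criteria):** adults with ventilation started in the ED or ICU. ARDS is not an exclusion. Same-day deaths and same-day transitions to comfort care are excluded.
- **ARDS as an aim:** outcomes in ARDS are a stated objective and the subject of Specific Aims #2 and #3. Aim #3 reports from 2014 data that "approximately 500 patients meet the criteria for" severe hypoxemia.
- **Scoring (Data Analysis, Primary Outcomes):** "death within 28 days of ICU admission will be counted as having zero VFD".
- **Sensitivity (Table 3):** three ICCs by three effect sizes, with the SD fixed throughout.

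**The concern.** The SD is the input to which the required sample size is most directly tied: with all else fixed, n grows with its square. It is borrowed from a population that leaves out a group the study deliberately includes. Patients with ARDS can be expected to have fewer and more variable VFDs, and every death by day 28 adds a value at the far end of the scale from a mean of 21.9. Both features widen the distribution.

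In the linear model of Equation 1 a lower baseline mean does not itself change power. The issue runs through the SD (and the ICC). If the true SD is materially above 7.8, the study could finish at its planned size, find no significant effect, and be read as evidence against a 1.5-day benefit when its power for that effect was well under 80%.

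**Working it through.** **1. The plan's own figure.** Inputs: effect 1.5 days, SD 7.8, one-sided 5%, 80% power, ICC 0.10.

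- With no clustering or time effects: n = 4 × (1.645 + 0.842)² × 7.8² / 1.5², which is 670 after rounding up per group. The stated 3,900 therefore reflects the clustered, time-adjusted design.
- Generalised least squares (GLS) version of Equation 1: hospital random intercept, quadratic time, a 0/1 exposure worth 1.5 days, and Table 5 cell counts (1,785 before and 2,342 after implementation, total 4,127) scaled to N. Power = Φ(1.5/SE − 1.645). At N = 3,900 the SE is about 0.52 if 7.8 is the total SD and 0.55 if it is the residual SD. Power is 89% and 86%, and the N for 80% is 2,891 and 3,215.

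This does not reproduce 3,900 exactly; the plan's figure is the more cautious one. Its simulation inputs (time coefficients, tidal-volume distribution, number of runs) are not given, and other specifications bracket it: categorical time, one-sided, needs 4,234 to 4,707. I do not call 3,900 an arithmetic error. Results below are given both ways: by GLS, and *calibrated*, meaning 80% at 3,900 with SD 7.8 is taken as exact.

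**2. What mean 21.9 and SD 7.8 can accommodate.** If a share p scores zero, the overall mean is 21.9 and the other patients have SD s, then

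variance = (1 − p)s² + [p/(1 − p)] × 21.9².

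Setting s = 0 gives p/(1 − p) ≤ 7.8²/21.9² = 60.84/479.61 = 0.127, so p ≤ 11.3%. With s between 6 and 3 the ceiling is 5.3% to 9.9%. This ceiling has to cover deaths by day 28 plus any survivors never liberated from the ventilator.

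**3. SD under assumed zero shares.** The document gives no mortality, so these shares are assumptions. SD = √[(1 − p)s² + p(1 − p)m²], with other patients at mean m = 22, SD 6, or m = 24, SD 4.

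| Zero share | SD (22, 6) | SD (24, 4) | GLS power at 3,900 | Calibrated power at 3,900 |
|---|---|---|---|---|
| 10% | 8.72 | 8.14 | 79-87% | 72-77% |
| 15% | 9.61 | 9.33 | 72-78% | 65-67% |
| 20% | 10.31 | 10.24 | 67-71% | 59-60% |
| 25% | 10.85 | 10.95 | 62-67% | 55-56% |
| 30% | 11.26 | 11.50 | 58-64% | 52-53% |

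Calibrated power = Φ(2.486 × 7.8/SD − 1.645). Taking SD 9.4 to 11.4 as the central span for 15-30% zeros:

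- GLS: 77% down to 59%.
- Calibrated: Φ(2.063 − 1.645) = 66% down to Φ(1.701 − 1.645) = 52%. The N for 80% is 3,900 × (SD/7.8)², about 5,700 to 8,300, and the effect detectable at 3,900 is 1.5 × SD/7.8, about 1.8 to 2.2 days.

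**4. SD from mixing in ARDS patients.** Assume ARDS in 10-30% of patients with VFD mean 12-16 and SD 10-10.5, and 21.9/7.8 in the rest. The overall SD is 8.2 to 9.8. Power at 3,900 is 70-86% (GLS) or 63-76% (calibrated).

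**5. Margin.** GLS keeps 80% at 3,900 up to an SD of about 8.6 (residual) to 9.05 (total). In the calibrated version the expected enrolment of about 4,000 absorbs an SD of only 7.8 × √(4,000/3,900) = 7.9.

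**The case against.** - **The source may already score deaths as zero.** This stands. The protocol does not say how the meta-analysis handled deaths, and 21.9/7.8 leaves room for up to 11.3% zeros. The exclusion of same-day deaths and comfort care also removes some early zeros. A reader might infer a direct conflict between the source figures and the scoring rule; the document does not show one unless more than 11.3% of enrolled patients score zero.
- **The power loss depends on chosen assumptions.** This also stands. No mortality, ARDS share or local SD is given. At 10% zeros, and in part of the ARDS mixtures, the GLS version still reaches 80%. The calibrated figures rest on a scaling that the plan does not state.
- **About 500 severely hypoxemic patients is not an ARDS count.** Correct. Against 3,421 patients in Table 4 it is about 15%, but ARDS also requires the imaging and clinical criteria described under Specific Aim 3, and the Significance section says ARDS was not determined in the baseline data. It does not establish that 15% of patients have ARDS.
- **The representativeness statement may refer only to tidal volume.** On that feature it is fair: 2,330 of 2,997 patients in Table 1 (78%) lie above 6 and up to 10 ml/kg. But a match on tidal volume says nothing about the spread of VFD, which is what the calculation borrows.

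None of this supplies a reason why an SD from patients without ARDS should apply to a study that includes them.

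**Conclusion.** The point holds as a lack of justification. The SD of 7.8 comes from a population that differs from the enrolled one in a way the protocol itself makes central, and no sensitivity to the SD is shown. The stated 80% power at about 3,900 is likely, though not proven, to be too favourable.

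Its size depends on assumptions the document cannot settle. With 15-30% of patients at zero (SD about 9.4-11.4), power at 3,900 would be about 59-77% by GLS or about 52-66% if the plan's 80% is exact. If the SD stays below about 8.6-9.05, the GLS version still supports 80%.

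A reader might go further and conclude that the study is underpowered or that 3,900 is wrong. The document does not support either: the first needs a mortality or SD it does not give, and the second needs simulation inputs it does not report.

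**What to change.** 1. Estimate the mean and SD of VFD in the sponsor's own pre-implementation patients, ARDS included, using the protocol's 48-hour unassisted-breathing definition, its zero score for deaths and its same-day exclusions.
2. Rerun Table 3 with that SD, and over a range such as 7.8 to 11.5.
3. Restate power, or the difference detectable with 80% power, at the expected enrolment of about 4,000.
4. Limit the representativeness statement to the tidal-volume range.

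**Cost:** one data extraction and a rerun of the simulation. The listed data elements include intubation and first ventilator-check dates but no explicit end-of-ventilation date, so the extraction may take some work. The study must derive VFD for its own baseline period in any case. The stated power may become less favourable. No extra patients are needed, because the change restates precision for a rollout whose timing is already set.

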Efficacy of a high PEEP strategy for patients requires identifying patients with moderate or severe ARDS, determining protocol compliance, and measuring outcomes. Determination of ARDS using the Berlin Definition²³ requires acute respiratory failure not fully explained by cardiac failure or fluid overload within one week of a known clinical insult, bilateral opacities on chest radiology imaging not fully explained by effusions, lobar/lung collapse, or nodules, and $PaO_2/FIO_2 \le 300$ mm Hg with PEEP or CPAP ≥ 5 cm H₂O. Applying these criteria to identify ARDS in a large pragmatic study with a target enrollment of approximately 3,500 patients is a significant challenge. We will focus on defining ARDS among those patients with mild, moderate, or severe hypoxemia as defined by a PaO_2 to FIO_2 ratio ≤ 300 and evaluate chest radiographs for bilateral infiltrates in that group. Then we will evaluate implementation of the high PEEP strategy and outcomes in the group of patients with ARDS who have a PaO_2 to FIO_2 ratio ≤ 200 . Even though a high PEEP strategy is recommended for moderate to severe ARDS as

defined by a PaO₂/FIO₂ ≤ 200, this is not strictly applied clinically based on our review of ARDS Network study data (**Figure 2**). Implementation of the high PEEP protocol for moderate to severe ARDS is left up to the clinician in the computerized mechanical ventilation protocol. By performing a sub-group analysis we will characterize the utilization of a high PEEP strategy in patients with moderate or severe ARDS at Intermountain Healthcare hospitals. Lastly, the benefit of segmenting the data into categories "mild", "moderate", and "severe" hypoxemia, is that it will allow our team to use a stratified Kaplan–Meier curve to assess differences in mortality using log rank statistics. This will directly show the relationship between hypoxemia, treatment and mortality. New findings from Specific Aim #3 may drastically influence the standard of care within Intermountain Healthcare and internationally.

Research Strategy for Specific Aim 4

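### Aim 3 tests whether high PEEP improves outcomes with survival curves controlled only by PaO2/FiO2 class, although clinicians choose PEEP; the comparison is confounded by indication and cannot show efficacy

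*Protocol*

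**What the plan says.** Specific Aim #3 sets out to "evaluate protocol implementation of the high versus low positive end expiratory pressure (PEEP) protocol and assess relationship with patient outcomes". Its hypothesis is causal in form: "A high PEEP strategy in patients with moderate to severe hypoxemia and ARDS will improve outcomes". PEEP strategy is not allocated: "Implementation of the high PEEP protocol will be based upon clinician discretion". Research Strategy for Specific Aim 3 repeats this: "Implementation of the high PEEP protocol for moderate to severe ARDS is left up to the clinician".

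The same section opens in the language of efficacy: "Efficacy of a high PEEP strategy for patients requires identifying patients with moderate or severe ARDS, determining protocol compliance, and measuring outcomes". The only method it names is to "use a stratified Kaplan–Meier curve to assess differences in mortality using log rank statistics", with mild, moderate and severe hypoxemia as the segments. It then concludes: "This will directly show the relationship between hypoxemia, treatment and mortality". It adds that the findings may drastically influence the standard of care, locally and internationally.

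Patient-level covariates, hospital random intercepts and quadratic time effects appear under Data Analysis, in the paragraph on the mixed model of initial tidal volume on ventilator-free days. Nothing extends them to PEEP and mortality. No time origin, exposure window or rule for changes of PEEP strategy is given for Aim 3.

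**The concern.** The background section offers high PEEP as the alternative for moderate to severe ARDS, so its use follows severity by design. Stratifying by PaO2/FiO2 class controls that only coarsely. The moderate class runs from 101 to 200, and within it clinicians may well choose high PEEP for patients whose prognosis differs. Age, diagnosis, hospital and period are not controlled either. The computerized option also arrives hospital by hospital with iCentra, so its use may track site and calendar time.

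A difference between the curves, or its absence, would then mix any PEEP effect with the reasons for choosing PEEP. Hypothesis 3 would get a biased answer, presented as direct evidence and as a possible reason to change care.

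A second risk depends on a definition the protocol does not give. If patients were classed as ever on high PEEP and followed from the start of ventilation, those who died before high PEEP was started would count as low PEEP. That would favour high PEEP artificially.

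**Working it through.** The protocol gives no event rate, effect size or power for Aim 3, so there is no figure to reproduce. The checks below show what the named method does when high PEEP has no effect at all.

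**1. Confounding by indication, one hypoxemia class**

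*From the protocol:* 500 patients, the approximate 2014 count with severe hypoxemia (Specific Aim #3); deaths on the day of admission excluded (Exclusion Criteria), approximated by removing deaths in the first 24 hours.

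*Assumed:* 90-day mortality of 35% at average severity, Weibull shape 0.7, about 30% on high PEEP, and within-class severity u ~ N(0,1) with the same factor f per SD on the hazard of death and on the odds of high PEEP.

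- Survival: S(t | u) = exp(−λ t^0.7 f^u), with λ = −ln(0.65)/90^0.7 = 0.431/23.3 = 0.0185
- Choice: logit P(high PEEP | u) = ln(0.3/0.7) + u ln f
- Test: Z = (O − E)/√V, two-sided 5%

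| f per SD | Apparent HR (true value 1) | False rejection, n = 500 |
|---|---|---|
| 1.3 | about 1.07 | about 7% |
| 1.5 | about 1.17 | about 16% |
| 2.0 | about 1.54 | about 74% |

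Before the exclusion is applied, the rejection rates are nearly the same (6%, 16% and 72%). With 1,000 patients, a size the protocol does not give, they are about 9%, 26% and 95%.

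**2. The planned stratified test, two classes**

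500 moderate and 500 severe patients, assumed 28-day mortality of 25% and 40%, first-day deaths removed, log-rank stratified by class, true HR 1, PEEP chosen on day 1 (about 40% high):

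- Choice unrelated to severity: HR 1.01, rejection about 4%.
- Severity OR 1.5 for choice and HR 1.5 for death: apparent HR 1.16, false harm in 25%.
- Severity OR 2 for choice and HR 1.5 for death: apparent HR 1.30 to 1.31, false harm in 62–65%.
- The same OR 2 and HR 1.5, with strata for deciles of within-class severity added: HR 1.02, rejection about 5%.

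Stratifying by class therefore leaves the within-class bias in place; adjusting for severity removes it when severity is measured.

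**3. Immortal time, if exposure were ever high PEEP counted from the start of ventilation**

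Assumed: 30-day mortality 35%, Weibull shape 0.7, half the patients intended for high PEEP, exponential time to its start, no true effect. The 30-day mortality gap in favour of high PEEP is:

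| Mean start | No exclusion | Deaths in first 0.5–1 day removed |
|---|---|---|
| 0.25–0.5 day | – | 0–0.7 points |
| 1 day | about 4.6 points | 1.1–2.0 points |
| 2 days | about 7.3 points | 3.4–4.6 points |

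With the same-day exclusion the gap is thus about 0 to 5 points. It depends on how late high PEEP may start and still count. In the two-class simulation the false HR is 0.94 for a 3-day window, 0.81 for 7 days and 0.63 for 14 days, and about 1.01 when exposure is fixed on day 1.

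**4. Do both problems need handling?**

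With a 7-day window, OR 2 and HR 1.5, treating PEEP as time-dependent but not adjusting for severity still gives HR 1.38, with rejection in 79%. Adding severity strata brings it to 1.02.

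**The case against.** **The analysis is not wholly unadjusted.** This stands. PaO2/FiO2 class partly controls the stated basis for recommending high PEEP. What is left uncontrolled is everything within the class and beyond oxygenation.

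**Immortal time is not in the text.** This stands too. A reader might infer that anyone who dies early falls into the low-PEEP group, and that the false gap is 4 to 7 points. The documents support neither. Nothing defines exposure as ever high PEEP from day 0; only deaths before high PEEP starts would be misplaced; and 4 to 7 points appears only if the same-day-death exclusion is ignored. An exposure window could also be set in a statistical analysis plan.

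**The size and direction of confounding are assumed.** Correct. At 1.3 per SD the test is close to its nominal level. A reader might infer that high PEEP is bound to look harmful, but the protocol says only that uptake is inconsistent. The 500 patients are also hypoxemia cases, not confirmed ARDS.

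**The compared factor is unclear.** The curves are described by hypoxemia class, so it is not certain that the log-rank test compares PEEP strategies. That is a separate ambiguity. If it does not compare them, no test is named for Hypothesis 3 at all.

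**The aim is secondary and descriptive.** The Aim 3 heading speaks of characterizing implementation, and the study is called observational. But Hypothesis 3, the efficacy wording and the claim of direct evidence go beyond description. The protocol itself fixes both the method and the interpretation, so this is not detail left to a later plan.

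**Conclusion.** The point holds for confounding by indication. Curves and a log-rank test controlled only by PaO2/FiO2 class, with PEEP chosen by clinicians, cannot establish efficacy or directly show a treatment effect on mortality. Under a true null, false rejection ranges from near nominal (about 7%) to about 74% with 500 patients, as the assumed severity effect rises from 1.3 to 2.0 per SD. These figures illustrate sensitivity; the protocol supplies no data on the strength or direction of the confounding.

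Immortal time is conditional. It is negligible if exposure is fixed on day 1, about 0 to 5 points of 30-day mortality for mean starts of up to 2 days, and larger if late starters count. It would work in favour of high PEEP, whereas confounding by worse prognosis would work against it, so the two could partly cancel. The primary ventilator-free-day result is not affected. The change should be made because the protocol says Aim 3 may alter care.

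**What to change.** In Specific Aim #3 and Research Strategy for Specific Aim 3:

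- Assess Hypothesis 3 in ARDS patients with PaO2/FiO2 of 200 or less with a Cox model for mortality. Classify PEEP strategy at a fixed landmark, for example 24 hours after ventilation starts, in patients alive and ventilated then, and count follow-up from the landmark.
- Stratify by moderate and severe. Adjust for the PaO2/FiO2 value, FiO2, age, diagnosis, hospital and calendar time, plus a severity measure if one can be extracted.
- Keep the Kaplan-Meier curves as description.
- Replace the efficacy and direct-evidence wording with adjusted association.

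In Data Collection, add timed PEEP values. Research Strategy for Specific Aim 4 mentions PEEP among the data queries, but the extraction list contains neither PEEP, its timing nor a general severity score. Age, diagnosis codes, hospital, admission date, FiO2 and PaO2/FiO2 are already listed.

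The cost is one added data field, one added model and some rewording. Patients who die before the landmark leave this comparison. Residual confounding remains, especially without a severity score, so the result must be reported as an association.

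### The only blood gas on the data list is the first of the hospital stay, not tied to ventilation or PEEP, so the ARDS group and hypoxemia classes of Aims 2 and 3 can rest on a pre-ventilation sample

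*Protocol*

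**What the plan says.** Under Specific Aim #3 the protocol states that "Patients with ARDS will be analyzed based on hypoxemia conditions", in three PaO2/FiO2 bands: 201-300, 101-200 and 100 or less. No blood gas and no time window are named.

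Research Strategy for Specific Aim 3 describes the Berlin definition: onset "within one week of a known clinical insult", bilateral opacities, and a ratio of at most 300 "mm Hg with PEEP or CPAP ≥ 5 cm H₂O". It then adds: "Applying these criteria to identify ARDS in a large pragmatic study with a target enrollment of approximately 3,500 patients is a significant challenge". The working approach follows: "We will focus on defining ARDS among those patients with mild, moderate, or severe hypoxemia", taken as a ratio of 300 or less, and "evaluate chest radiographs for bilateral infiltrates in that group". The PEEP condition is neither repeated nor withdrawn. The section continues: "Then we will evaluate implementation of the high PEEP strategy and outcomes in the group of patients with ARDS who have a" ratio of 200 or less.

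The Waiver of Authorization section points to the Data Collection list as the statement of what the study will collect. The one blood gas on that list is the "Initial Arterial Blood Gas recorded during hospital stay". PaO2 (measured and corrected), FiO2 and PaO2/FiO2 come directly after it. The list includes an intubation date, but no date or time for the gas, no PEEP and no radiograph reading. Research Strategy for Specific Aim 4 says that PEEP and FiO2 will be queried, but does not link them to the gas.

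**The concern.** Patients enter the study when ventilation starts in the emergency department or ICU. The first gas of a hospital stay has no fixed relation to that moment: it may be drawn on a mask before intubation, on a ward days earlier, or on the ventilator. A ratio from a patient not yet on PEEP or CPAP does not measure what the Berlin criterion measures.

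Three things depend on this ratio: who is in the ARDS group of Aim 2, which Kaplan-Meier stratum a patient falls into in Aim 3, and who counts in the denominator of a listed secondary outcome, the use of a high PEEP strategy at a ratio of 200 or less. If the gas is mistimed for some patients, all three groups mix people classed on different bases, and the listed data would not let an analyst tell which is which.

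**Working it through.** The plan gives no figure to reproduce, so the check compares the definitions with the data list.

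1. **What classification needs.** The three bands need a PaO2/FiO2 from an identified gas. If the Berlin oxygenation criterion applies, they also need the PEEP or CPAP at that draw. The ARDS label needs a radiograph reading as well.

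2. **What the list supplies.** One gas, the first of the stay, with PaO2, FiO2 and the ratio. It supplies no draw time, no PEEP and no radiograph item. An intubation date is listed, but with no date for the gas the two cannot be put in order.

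3. **What happens if the listed gas is used.** Three cases arise:
   - Drawn before ventilation. The PEEP or CPAP condition is not assured. It could be met by a patient on mask CPAP of 5 or more, but no value is listed to show it.
   - Drawn on the ventilator at PEEP of 5 or more, before any high-PEEP strategy. The criterion is met and the class is sound.
   - Drawn on the ventilator after PEEP was raised. The ratio may already reflect the exposure that Aim 3 studies.

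   The list holds nothing that separates these cases.

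4. **How a class can change (hypothetical patient).** A mask gas with PaO2 60 on FiO2 0.6 gives 60/0.6 = 100, which is severe. After intubation, PaO2 130 on FiO2 0.6 gives 130/0.6 = 217, which is mild and outside the group at 200 or less. The same patient would enter or leave the high-PEEP denominator according to which gas is read. This shows the mechanism, not its frequency.

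5. **Size.** The protocol does not give the share of first gases that precede ventilation. As an assumption it could lie anywhere from 0% to 100%. Applied to the roughly 500 patients with severe hypoxemia reported for 2014, that is 0 to 500, which is uninformative. Those 500 are also not confirmed ARDS cases.

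6. **What is not touched.** The primary analysis models VFDs on initial tidal volume in all ventilated patients and does not use ARDS status.

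The classification is loose in one further respect: Process for Aim #3 defines three classes and then refers to four sub-groups.

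**The case against.** The strongest reply is that no section says the first gas decides ARDS status or severity, and that the list is visibly incomplete. It also omits PEEP, radiographs and the quality-of-life instrument, all of which the protocol says it will use. Absence from the list therefore does not prove that later gases will not be collected, and a statistical analysis plan could name the qualifying gas. This stands in part: use of the first gas is an inference from the list. But the list does more than stay silent. It names a specific gas, and that gas is poorly suited to the definitions elsewhere in the protocol.

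A reader might go further and infer that the Aim 2 and Aim 3 groups cannot satisfy a Berlin rule the protocol has adopted. The text does not support this. The protocol describes Berlin, calls its application difficult, and moves to a simpler rule. A first gas drawn on the ventilator at sufficient PEEP does meet the criterion. Nor does the one-week limit on onset say which gas to read.

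A reader might also want every gas over the first week searched, so that later ARDS is captured. That would add bias. Under the iCentra ventilator rules, ventilation instructions are issued only after a gas, so gases may become more frequent after implementation and more ARDS be detected for that reason alone. The Background section also holds that low tidal volume may reduce the development of ARDS, so later ARDS may be a result of the exposure, and selecting on it would distort Aim 2. Classification near the start of ventilation is the better principle. The defect is that the listed gas is not anchored there.

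**Conclusion.** The point holds in a limited form. The one blood gas specified for collection is not tied to ventilation, has no listed draw time and no concurrent PEEP, while the ARDS group and hypoxemia classes depend on a ratio for which the protocol itself describes a PEEP or CPAP condition. If that gas is the classifier, as its position on the list implies, some patients can be misassigned in the Aim 2 group, the Aim 3 strata and the high-PEEP denominator.

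This rests on two assumptions: that the listed gas is the one used, and that some first gases precede ventilation. The entry criteria allow the second, but the protocol does not quantify it, so no count of affected patients can be defended. The consequence is confined to Aims 2 and 3 and the related secondary outcome. The Aim 1 primary analysis stands as it is.

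**What to change.** Reconcile Specific Aim #3, Research Strategy for Specific Aims 3 and 4, and the Data Collection list:

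- Replace the listed item with the first arterial gas after the start of ventilation, within a short fixed window stated in the protocol and identical before and after implementation. For patients transferred after intubation, say which hospital's gas counts.
- List that gas's date and time, its FiO2, the PEEP at the draw, and the radiograph reading.
- State whether PEEP of at least 5 is required for the study's ARDS label or has been dropped.
- For Aim 3, flag gases drawn after high PEEP had begun and exclude them in a sensitivity analysis. A post-intubation gas is more exposed to this problem than an early one, which is why the PEEP value must be kept.
- Correct the number of hypoxemia sub-groups.

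The cost is a revised warehouse query, a few added lines in the data list and in the waiver request that relies on it, and some programming. No patient contact is needed. The downside is that patients with no gas in the window leave the ARDS subgroup. They should be counted and reported separately for the periods before and after implementation, since a difference between the periods would itself be a source of bias.
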